
phase is critical for determining the salient characteristics of a product or service. Typically, researchers use focus groups that consist of end-users or "experts", to learn from people who have the most experience with the service, but researchers also convene focus groups of people who have little or no experience with a service to learn what may be important for a new user. Focus groups typically are comprised of 6 to 10 participants who do not know one another and who have similar associations to the topic being investigated (i.e., newly diagnosed localized PCa patients). We will make an effort to recruit equal number of surgical and radiation treatment patients and men younger than age 65 and age 65. It is recommended that one conduct at least two focus groups to capture experiences from similar groups of individuals [254-256]. Drs. [name], [name], and [name] each have extensive experience in racial and ethnic disparity research and will carefully construct each focus group. Thus, we will conduct focus groups with good representation from minority and non-minority patients. Of the six patient focus groups, three will be with newly diagnosed patients yet to make treatment decision; and three will be with those who underwent treatment one year ago, providing additional insight into what they wish they had known about the less immediate outcomes and aspects of treatment. In contrast to individual interview, focus group participants relate their experiences and reactions among peers with whom they likely share some common frame of reference. The discussions stimulated in a group setting and listening to others' experiences has the potential to stimulate memories, ideas and experiences relevant to the topic at hand [254-256]. Overarching goal of focus groups is to obtain perspectives of two of the key stakeholders (patients and physicians) about those components or features of PCa care are important to consider in choosing a treatment. The most commonly mentioned and strongly weighted features of treatment across the focus groups will be used to create the conjoint task (to be used in Phase2). If saturation of emerging themes is not reached after six focus groups, we will conduct additional focus groups until saturation occurs. (See Appendix for interview guide that was developed using results of our prior focus group of physicians, discussed in preliminary work). (3) Assigning levels to the attributes. Levels of an attribute may be cardinal (e.g. waiting time, missed work), ordinal (e.g. level of pain) or categorical (e.g. surgery or radiation treatment). Attribute levels will be identified and aligned with the active surveillance (AS) and five active treatment options being studied (RP, RALP, BT, EBRT, PT), reviewed for appropriateness and wording by the study investigators and advisory board members. (4) Developing choice scenarios. Scenarios will describe services, treatment options and outcome configurations for the attributes and level chosen. We will use a fractional factorial design to reduce the number of paired comparisons to the smallest number necessary for efficient estimation of utility weights [49,183,188]. (5) Conjoint task instrument testing. We will pilot test the conjoint task instrument for appropriateness of attributes, levels, language and ease of administration in 20 PCa patients. PHASE 2 Study Population: We will use stratified randomized control trial to study association between value markers and objective (complications and cancer recurrence) and subjective (HRQoL, psychological wellbeing) outcomes across intervention groups, over 24 month period. We will recruit newly diagnosed localized PCa patients from UPHS (Hospital of University of Pennsylvania, Presbyterian Medical Center, and Pennsylvania Hospital), Fox Chase Cancer Center and Philadelphia Veterans Administration Medical Center (PVAMC) and randomize them to conjoint analysis intervention (n=360) or control group (n=360). D.2.1.1 Participants: The sample will consist of 720 newly-diagnosed PCa patients. Inclusion criteria are: (1) treated for PCa at UPHS, Fox Chase Cancer Center or PVAMC; (2) aged 45 years; (3) newly diagnosed with localized PCa and TNM stage T3a; (4) community dwelling; (5) Gleason score 8; (6) low (PSA 10 ng/ml, Gleason 6, clinical stage T1-2a), intermediate (PSA 10 -20 ng/ml, Gleason 7, clinical stage T2b), and high risk (PSA 20, Gleason 8, clinical stage T2c-3a) group [45] and (7) provide informed consent. Exclusion criteria are: (1) Distant, metastatic or un-staged PCa at diagnosis; (2) visited the clinics to obtain second opinion only; (3) moved to another location; (4) unable to communicate in English and (5) cognitive impairment (Mini Mental State Exam or MMSE score < 21). MMSE is a standardized mental status examination widely used for clinical and research purposes [197,198]. D.2.1.2 Recruitment and participant availability: Participants will be recruited from UPHS, PVAMC and Fox Chase Cancer Center's urology and radiation oncology clinics using recruitment protocols that we have successfully used in our prior and ongoing PCa studies. Recruitment will occur in seven steps: 1) determining potential eligibility; 2) obtaining consent from patients urologist/physician; 3) confirming eligibility; 4) screening via phone and interview to assess willingness to participate; 5) obtaining informed consent and HIPAA permissions; 6) baseline assessments; and 7) follow-up assessments. The study and consent form comply with HIPAA Standards for Privacy of Individually Identifiable Health Information. The draft study design and protocol have been approved by the University of Pennsylvania IRB. Future changes will be reviewed and approved prior to implementation. Participant availability: UPHS is a large hospital and physician network in greater Philadelphia area. Approximately 1,600 patients with newly diagnosed PCa are evaluated annually: 40-50% undergo surgery (RP or RALP); 30-40% undergo EBRT

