
or BT; 10-20% undergo PT. The urology clinic at PRINCIPAL INVESTIGATOR (LAST, FIRST, MIDDLE): [name] PCORI Research Plan: Research Strategy 9 the Hospital of the University of Pennsylvania (HUP) treats more than 60% of this group; the rest are treated at Presbyterian Medical Center and Pennsylvania Hospital. Additionally, UPHS has a proton therapy center, providing a unique opportunity to study this new technology. The Philadelphia Veterans Administration Medical Center (PVAMC) cares for 33,000 veterans in Philadelphia area and evaluates ~400 patients with newly diagnosed PCa each year. Fox Chase Cancer Center evaluates ~500 patients with newly diagnosed PCa each year. Together, UPHS, PVAMC, and Fox Chase Cancer Center provide care to socio-demographically diverse population of ~2,500 men newly diagnosed with PCa each year. Thus, our study sample requirement of 720 patients (33% of the available pool) can be fulfilled comfortably, as demonstrated by the successful recruitment for our earlier studies. Recruitment: Prior to study initiation, investigators will explain the study objectives to physicians who actively treat PCa at the UPHS, PVAMC, Fox Chase urology clinics. During a patient's initial visit, Drs. [name], [name], or [name] will briefly introduce the study to the patient. Each week, the research assistant will contact the participating physician offices to obtain contact information for those patients who have expressed an interest in the study. Potential participants will be contacted during their office visits, at which time those eligible may agree to participate and provide informed consent, request additional information and/or time to think or request to be contacted later. Patients who request to be contacted later will be sent study information, a consent form and a prepaid return envelope. Participants will discuss the consent form with research assistant prior to signing, at which time all questions will be answered. During enrollment, compensation of \$20 will be provided. Using a similar recruitment strategy in our prior PCa studies, we had achieved enrollment and retention rates of 85% or higher. The expected number of 60 participants in each treatment group (AS, RP, RALP, EBRT, BT or PT) will be achieved as follows: (1) each recruited participant randomly assigned to the conjoint analysis intervention group will meet with research assistant to complete the computer-based conjoint analysis tasks and other surveys before initiation of treatment or making a treatment decision; (2) after treatment decision is made, patients (both cases and controls) will be assigned to the appropriate group based on treatment; (3) this process will continue until we reach the required number of participants in each group. To achieve this, we may evaluate and obtain baseline data including conjoint tasks from patients in excess of the required 360 participant each in the intervention and control groups. Based on our prior prospective cohort studies, to fulfill sample requirement of 60 participant in each treatment group ($60 \times 2 \times 6 = 720$), allowing for attrition we expect to obtain baseline assessment including conjoint tasks for 800 participants (10% excess). The cohort that does not get assigned for further follow-up due to targeted group enrollment accrual will be analyzed to ensure comparability. D.2.2 Process of stratified randomization: We will recruit 720 participants stratified by three hospitals-UPHS, PVAMC, or Fox Chase Cancer Center (Figure 3). [name] will create randomization sequences for each hospital using a pseudo-random number generator with random blocking and will place the treatment assignments in sealed, opaque envelopes. All investigators, staff and referring physicians will be masked to the treatment assignment, except the research assistant who will open the envelope and notify participants of group assignment. Participants will be instructed not to reveal their group status to physicians or study personnel, except in case of emergency or if necessary for medical reason, which we believe to be unlikely. D.2.2.1 Conjoint analysis intervention The primary goal of patient-centered PCa care is to engage patients and their families in meaningful and thorough interactions with their healthcare providers to develop accurate and well-conceived treatment choice, using all available medical information appropriately, while also considering the medical, social and cultural needs and desires of the patient and family. It is important for providers to solicit patient preferences and not make assumptions about which treatment and associated side effects patients are more likely to prefer or feel is best for them. Results of conjoint analysis will be shared with the participants of the intervention group, family members, and treating physicians prior to treatment decision. D.2.2.2 Usual care controls: Participants from this group will receive usual care that consists of standard educational material about various treatment options. D.2.3 Data collection and follow-up: After obtaining informed consent, baseline data will be obtained in person prior to the initiation of treatment. Participants will meet with the research assistant to complete the PRINCIPAL INVESTIGATOR (LAST, FIRST, MIDDLE): [name] PCORI Research Plan: Research Strategy 10 computer-based conjoint analysis tasks. Patient identifiers will be removed to maintain data confidentiality. Only the PI will have access to the master files. For conjoint analysis, each participant will be asked to express his preference for attributes and attribute levels for active surveillance and five active treatments for clinically localized PCa (RP, RALP, EBRT, PT, BT) based on choice sets presented. The choices will vary based on the differing attributes of various treatments ascertained in prior work and focus groups. After pilot testing and refining the conjoint task in Phase 1, final attributes and levels will be used. Trade-offs

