
The following documents are currently attached to this item:

There are no documents attached for this item.

Analysis Plan

Analytic Methods General: The statistical analysis will proceed in three stages: First, we will check the data quality and carry out descriptive analyses of demographics and key outcome variables. Next, we will assess preferences using conjoint analysis and inferential analysis. For continuous outcome variables, we will check for homogeneity of errors using spread-vs.-level plots and will consider transforming variables that either are highly skewed or have variance that depends strongly on the mean. We will use methods based on general linear model (univariate and repeated-measures ANOVA, mixed models) to analyze uncensored continuous outcomes, such as generic and prostate-specific HRQoL, psychological wellbeing and satisfaction with care. For potentially censored outcome variables such as time to PSA recurrence, we will use Kaplan-Meier curves and Cox proportional hazard models. Poisson regression (zero-inflated) will be used for count data. We will use Bonferroni correction for multiple testing. We will use propensity-score and instrumental variable approach to minimize observed and unobserved bias within groups (i.e. intervention group and usual care control group). **Missing Data:** We will attempt to prevent missing data by ensuring that data collection is as complete as possible. Should there be substantial missing data, however, we will employ analysis and imputation methods to reduce bias and increase efficiency [279-282]. Based on the proportion of missing data, we will use complete-case analysis, or explore available techniques, such as standardized score imputation, simple means imputation, maximum likelihood model-based imputation, data augmentation, etc. [281]. When data are evidently non-missing at random, we will conduct explicit non-ignorable modeling and sensitivity analysis [278]. **Propensity score matching:** In observational studies, comparisons between treatment groups that do not adjust for factors associated with treatment choice may be biased. Propensity score technique offers a highly practical approach to address such bias [283]. Here, the probability of each participant being in the treatment arm (i.e., the propensity score), is estimated. Participants are sorted by their propensity scores; the sample is divided into strata based on estimated scores, the treatment effect within each stratum estimated and overall estimate computed by aggregating across strata in a weighted analysis. When the model for predicting treatment status includes all relevant covariates, within strata treatment groups will be balanced on all predictors and the overall comparison of treatment arms will have substantially lower bias. We will use a model relating PCa treatment (RP, RALP, EBRT, PT, BT or AS) to baseline factors [283-284]. To study the extent to which treatment groups are now matched, we will compare t-statistics for these covariates before and after adjusting for propensity score. This will be done separately for intervention group and usual care controls. **Instrumental variable analysis:** Another limitation of observational research is the strong potential for confounding bias, due to differences in comparison groups that are not reflected in the data (i.e., unobserved bias). The instrumental variable (IV) approach is useful in reducing this bias. This technique uses one or more observable factors that influence outcome only indirectly (the IV). This allows one to mimic randomization with different likelihoods of receiving a particular treatment [227, 285-291]. Physicians play an important role in patients treatment choice- a majority of the PCa patients report that their physicians recommendation was the most important factor in their treatment choice [11-12, 37-46, 51, 55-56, 60-64]. We will use specialty of the first physician (urologist, urologic oncologist, oncologist, radiation oncologist) who the patient saw during PCa diagnosis as an IV. We will explore other potential IVs, such as absolute distance between patients residence to the hospital where they will receive care (Hospital of University of Pennsylvania, Presbyterian Medical Center, PVAMC, Pennsylvania Hospital, or Fox-Chase Cancer Center). Validity of the IV(s) is assessed as following. First, we will use Pearsons correlation coefficient to examine the correlation between IV, primary exposure (treatment) and outcomes. We will then perform a partial F-test using a linear regression where treatment group is regressed on physician specialty along with patient attributes. For a valid IV, test statistic should be very high (e.g., physician specialty will strongly predict treatment after adjusting for covariates). Next, we will perform a partial F-test using a linear probability model in which HRQoL outcomes are regressed on specialty and patient demographic and clinical variables. For an IV to be valid, this test statistic should be very low. Finally, we will compare observable attributes across patient groups cared for by different physician specialty (initial). For the IV be valid, these groups should have comparable observable attributes. **Phase 1 Focus group analysis-development of conjoint task instrument:** The goal of focus groups is to identify attributes of PCa treatment that are most salient to localized PCa patients. This process includes following steps: (1) identifying and defining attributes; (2) assigning attribute levels; and (3) creating scenarios and choice sets. Attributes will be defined based on input from patient focus groups, literature, our prior research, and prior physician focus group. Once an attribute and its extreme values are defined, we will assign them appropriate levels. A large number of possible combinations of attributes and levels will preclude

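### The strength of the physician-specialty instrument is judged by a patient-level F-test that ignores clustering by first physician, so a weak instrument can look strong

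*Combined protocol and SAP*

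**What the plan says.** All of this is in the instrumental variable paragraph of the Analysis Plan (Combined protocol and SAP), unless another place is named.

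- **Instrument:** "We will use specialty of the first physician (urologist, urologic oncologist, oncologist, radiation oncologist) who the patient saw during PCa diagnosis as an IV".
- **Reason for it:** "a majority of the PCa patients report that their physicians recommendation was the most important factor in their treatment choice".
- **Strength check:** "We will then perform a partial F-test using a linear regression where treatment group is regressed on physician specialty along with patient attributes". The criterion is "For a valid IV, test statistic should be very high". No cut-off or significance level is given.
- **Outcome check:** "we will perform a partial F-test using a linear probability model in which HRQoL outcomes are regressed on specialty and patient demographic and clinical variables", with the criterion "For an IV to be valid, this test statistic should be very low".
- **Where it applies:** the opening paragraph of the Analysis Plan uses propensity scores and instrumental variables within the intervention group and within the usual care group. That points to about 360 men per analysis out of the total: "The sample will consist of 720 newly-diagnosed PCa patients" (Study Design).
- **Recruitment:** "Each week, the research assistant will contact the participating physician offices to obtain contact information" (Study Design, Recruitment).

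No section mentions correlation among men who share a physician. The mixed model for Specific Aim 3 has participant-level random effects and fixed effects for arm and hospital. The intra-class correlation of 0.3 in the sample-size text (Accrual) concerns repeated measures on one man, not men within a physician.

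**The concern.** Specialty belongs to the physician, not to the patient. The independent information on whether specialty predicts treatment therefore comes largely from the number of physicians. An ordinary partial F-test counts men who share a physician as independent observations.

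This is harmless only if, once specialty is known, men with the same first physician are no more alike in treatment than other men. The plan's own rationale makes that doubtful. If the physician's recommendation is what mainly moves patients, two physicians of one specialty with different habits produce correlated treatment among their patients. Such differences between individual physicians enter the between-specialty mean square and raise F even when specialty itself predicts nothing.

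Because the plan accepts the instrument when F is large, the error runs in the unsafe direction: a weak instrument can be accepted as strong. IV standard errors that ignore physician would also be too small, to the extent that outcome residuals share a physician component.

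**Working it through.** The documents give no F, cut-off, physician count or physician-level ICC for this analysis, so there is no figure of the plan's own to reproduce. The check asks how an ordinary F-test behaves when specialty has no effect.

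**Inputs from the documents**
- Four specialties, hence 3 numerator degrees of freedom.
- 360 men per arm.
- The 0.05 level appears only in the power calculation. It is borrowed here as the nominal level.

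**Assumptions (not in the documents)**
- Number of first physicians J: 12 to about 150.
- Within-physician ICC of treatment, given specialty: 0.01 to 0.20.

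**Step 1: design effect.** With m = 360/J men per physician, DEFF = 1 + (m − 1) × ICC.
- J = 20: m = 18; at ICC 0.05, DEFF = 1 + 17 × 0.05 = 1.85.
- J = 40: m = 9; at ICC 0.05, DEFF = 1 + 8 × 0.05 = 1.40.
- J = 150: m = 2.4; at ICC 0.05, DEFF = 1 + 1.4 × 0.05 = 1.07.
- J = 20 at ICC 0.01: DEFF = 1 + 17 × 0.01 = 1.17.

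**Step 2: closed-form approximation.** The 5% critical value of F(3, 356) is 2.63. With equal caseloads the patient-level F is roughly DEFF × χ²₃/3, so the rejection rate is about P(χ²₃ > 3 × 2.63 / DEFF).
- J = 20, ICC 0.05: 7.89/1.85 = 4.26, giving 23%.
- J = 40, ICC 0.05: 7.89/1.40 = 5.64, giving 13%.
- J = 150, ICC 0.05: 7.89/1.07 = 7.37, giving 6%.
- J = 20, ICC 0.01: 7.89/1.17 = 6.74, giving 8%.

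**Step 3: simulation.** There were 2,000 trials per setting in the two main set-ups, one with men spread evenly at random over physicians and one with unequal caseloads. The outcome was a physician effect with variance equal to the ICC plus patient error, with total variance 1 and no specialty effect. Ranges below cover separate runs. Single figures come from one run, except where marked 'about'.

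| Physicians (360 men) | ICC 0.01 | ICC 0.05 | ICC 0.20 |
|---|---|---|---|
| 12 | 12% | 38–42% | 80–82% |
| 20 | 10% | 25–31% | 69% |
| 40 | 7% | 15–18% | 52% |
| 100 | 6% | 11% | 27% |
| about 150 | – | about 8% | – |

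The simulated rates sit somewhat above the closed form because caseloads vary. With 20 physicians and unequal caseloads, the mean F under no specialty effect, which should be about 1, is 1.25 at ICC 0.01, 2.22 at ICC 0.05 and 5.67 at ICC 0.20. The corresponding design effects are 1.17, 1.85 and 4.40.

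**Step 4: the same test on physician means.** With unequal caseloads the rejection rate was 3.5–6.0% in every setting simulated. At ICC 0 the patient-level test is also correct (4–6%), so the excess comes from the clustering.

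**Limits.** The simulation used one continuous outcome without covariates. The plan has six treatments and adjusts for patient attributes. The bias in IV standard errors was not computed, because the plan states no IV estimator or standard error.

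**The case against.** **The size rests on two unknowns.** This stands. The instrument concerns the first physician seen during diagnosis, and nothing says these are the physicians in the participating offices. The recruitment text mentions referring physicians separately, so first physicians could be many. With about 150 of them the problem nearly vanishes at ICC 0.05.

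**A specialty effect of zero is a worst case.** The conceptual framework in the Background says physicians tend to recommend treatments from their own specialty. That is fair, and the rates above are not forecasts for this trial. They are a calibration check. The noise part of F is inflated by about the design effect whether or not specialty matters, so F overstates strength in either case.

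**Ordinary errors are inferred from silence.** Also true. The text does not exclude clustered errors. But the plan spells out its correlation structure for the longitudinal outcomes and names none here.

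**The stronger reading.** A reader might infer that both validity tests reject far too often, so that a valid instrument would be discarded through the HRQoL test. The documents do not support this. The statement about physician recommendations concerns treatment choice only, and nothing establishes that HRQoL is correlated within first physician after adjustment. That test also has a separate fault: if specialty strongly predicts treatment and treatment affects HRQoL, a valid instrument should predict HRQoL through treatment. Clustering does not repair that.

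Nor do the documents support describing the problem as a breached error rate or a passed F threshold, because the plan sets neither. Figures for 720 pooled men would not match an analysis described as within arms.

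**The reach is limited.** This stands. The Specific Aim 3 comparison is randomized and by intention to treat, and it does not use this instrument.

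**Conclusion.** The point holds for the first-stage strength test. The instrument varies only between physicians, the test as described treats men as independent, and the plan's own rationale makes within-physician correlation of treatment plausible. If that correlation is positive, F is inflated roughly by the design effect and instrument strength is overstated.

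The inflation could be serious or slight, depending on physician numbers and an ICC that must be obtained or assumed. For one arm the false-positive rate is about 25–31% with 20 physicians and 15–18% with 40 at ICC 0.05. It is about 5–10% at ICC 0.01 with 20 or more physicians, or at ICC 0.05 with about 150.

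The IV standard errors need the same protection, but the size of that error is not quantified. The conclusion does not extend to the HRQoL test, the exploratory distance instrument (which varies by patient) or the randomized comparison. It should be corrected before the IV analysis is run. It does not threaten the trial's main inference.

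**What to change.** In the instrumental variable paragraph of the Analysis Plan:

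1. Record a coded identifier for each man's first physician, and report the number of first physicians per specialty.
2. Replace the ordinary first-stage partial F with a physician-level test, or with one clustered by first physician and corrected for few clusters (for example a wild cluster bootstrap, or a random physician effect with small-sample degrees of freedom). Of these, only a test on physician means was checked here.
3. Set the strength threshold in advance.
4. Use the same clustering for the standard errors of the IV treatment effects.

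Do not present clustering as a repair of the HRQoL test, whose logic needs its own review.

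The cost is one coded variable and a few sentences. The price is a smaller F and wider IV intervals, and with few physicians the instrument may be found too weak to use. If first physicians are many and the correlation is negligible, results will barely change.
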